7.2 Exclusion criteria

Those who do not meet any of the above conditions are excluded.

Rationale: Included glioma, other brain tumors, and normal samples should be statistically significant and the conclusions obtained are scientifically valid. The selection of subjects for this study, while excluding research-related influencing factors, has no adverse effect on the health of the subjects.

7.3 Rejection Criteria

- (1) Samples considered by the researcher to be unsuitable for continuing clinical trials, such as samples that have not been prepared in accordance with the required steps.
- (2) Samples with unqualified genomic DNA quality, such as:
 - ① DNA concentration is less than 10ng/μL;
 - ② Genomic DNA was severely degraded or had insufficient purity, and OD260/OD280 exceeded the range of 1.6~2.0.
- (3) Samples whose repeated test results of reference methods failed.
- (4) Samples with incomplete clinical basic information (patients' visiting No. / medical record No./specimen No., age, sex, pathological diagnosis result).

8 Provisions for amendments to clinical trial protocols

Any modification to the protocol during the test should be explained, and the time, reason, process and record of the modification should be elaborated in detail, and its impact on the evaluation of the whole study results should be demonstrated.

9 Ethical issues and explanations of clinical trials

This clinical trial verification test uses the patient's pathological specimens in the previous treatment process. It is limited to in vitro diagnosis, does not directly contact the patient, does not cause any harm to the patient, and only compares the performance of the reagent with the control reagent. The results are only used for study and analysis related to this test, and will not guide the diagnosis and treatment of patients based on this, so it will not have any adverse effects on the human body.

This clinical trial strictly complies with the "Declaration of Helsinki", and this clinical verification trial involves relevant patient data. Such as: Patient visiting No. / medical record No. / specimen No., age, sex, pathological diagnosis result, etc. The hospital and Genetron Health (Beijing) Co., Ltd. will jointly undertake the confidentiality of the patient information, and the clinical trial operator and clinical validation unit promise not to disclose the content related to the subject specimen.

Therefore, the clinical trial was verified to submit an informed consent exemption to the ETHICS Committee.

10 Data processing and record keeping

It is required to keep all experimental records during the clinical trial, the results should be objective, timely and serious, and the operator and operation time should be recorded. Medical institutions shall keep the clinical trial data for five years after the termination of the trial.

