3.3 Study technology route

3.4 Quality control method

- (1) The clinical verification institutions are all three-level medical institutions above the provincial level with the ability to conduct the clinical research technology and equipment to ensure the quality of clinical diagnosis.
- (2) Each clinical trial institution has 1 project director, and 1 to 3 fixed project members. Strictly follow the requirements of the clinical trial protocol. The reporting institution appoints 1 inspector to monitor and cooperate with the team leader institution and the trail institution at any time. The technical personnel of the team leader institution keep close contact with each trail center at any time.
- (3) The test kit detection and reference method detection are carried out in accordance with the blind method.
- (4) Hospital laboratories participating in clinical trials should establish standard operating procedures and quality control procedures for experimental observation indicators. The test report must be complete, which must include date, test items, test results and their normal range. The person concerned should sign. Each test is set up control, and strictly in accordance with the requirements of the manual.
- (5) Training: Before the start of the experiment, conduct protocol training for all personnel participating in the experiment, and conduct training and assessment for clinical research staff, so that clinical trial personnel able to quickly become familiar with and master the fluorescence PCR technology and the applicable instruments, operating methods, and technical performance etc. of the kit.
- (6) This protocol has been determined through repeated communication and research between the experimental institution and the clinical institution, and must be strictly implemented. Any changes in the plan must be approved by the team leader (master) institution.

4 Evaluation method

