4.3 Evaluate the conformity between the kit and the reference method

- (1) If the results to be tested and the reference results are both positive or negative, it is regarded as in conformity.
- (2) In the event that the result to be tested is positive and the reference result is negative, or the result to be tested is negative and the reference result is positive, it is recorded as non-conformity.
- (3) If the result to be tested fails and the reference method has confirmed results, it shall be recorded as non-conformity. The reasons and results of the non-conformity shall be truthfully recorded, and the comparison results shall be repeatedly confirmed when necessary.
- (4) Complete subsequent statistical analysis based on the above statistical results.

5 Statistical methods

Statistical analysis of clinical study data: Kappa test was used for statistical analysis of the comparison between the kit test results and gene sequencing test results, and then the difference between the results obtained by the two methods was compared. If $\text{Kappa} > 0.6$, it was proved that there was no statistical difference between the two methods in detecting IDH1 gene mutations in glioma samples.

6 Duration of clinical trials and its reasons

The clinical study lasted about 6-8 months from the drafting of the protocol, project approval, ethical review, agreement signing, specimen collection, the beginning of the test to the end of the trial, and the report and seal are completed. If the sample collection is smooth and the number of samples meets the test requirements, the clinical trial time can be shortened; if it is not smooth, the time can be appropriately extended.

7 Inclusion criteria, exclusion criteria and rejection Criteria

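### Section 7.3(1) lets the researcher reject unsuitable samples without requiring the decision to precede, or be blind to, the results, so result-informed removal that would raise agreement and Kappa is not prevented

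*Combined protocol and SAP*

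**What the plan says.** All references are to the combined protocol and SAP.

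- **Section 7.3(1), rejection by judgement.** The rule covers "Samples considered by the researcher to be unsuitable for continuing clinical trials". The one example concerns faulty preparation and is introduced as an example only. No time point, blinding condition or second reader is given.
- **Section 7.3(2), DNA quality.** There are numeric limits (concentration below 10 ng/μL; OD260/OD280 outside 1.6 to 2.0). The list is again open, and severe degradation has no numeric limit.
- **Section 7.3(3), reference failure.** The rule rejects "Samples whose repeated test results of reference methods failed". This can be known only after testing.
- **Section 4.3(2), discordant pairs.** For one direction of disagreement the text reads "or the result to be tested is negative and the reference result is positive, it is recorded as non-conformity"; the opposite direction is treated the same way.
- **Section 4.3(3), failed kit runs.** "If the result to be tested fails and the reference method has confirmed results, it shall be recorded as non-conformity". It continues: "The reasons and results of the non-conformity shall be truthfully recorded, and the comparison results shall be repeatedly confirmed when necessary".
- **Section 3.4(3), blinding.** "The test kit detection and reference method detection are carried out in accordance with the blind method". Section 3.1 adds coding of cases and independent determination of results.
- **Section 5, success criterion.** If Kappa exceeds 0.6, "it was proved that there was no statistical difference between the two methods in detecting IDH1 gene mutations in glioma samples".
- **Section 10, records.** All experimental records are to be kept. No section defines an analysis set or asks for a table of rejected samples.

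**The concern.** In a method-comparison study the estimate depends on which pairs stay in the table. Rejecting samples for reasons unrelated to the results does no harm: if concordant and discordant pairs are lost at the same rate, expected agreement is unchanged. The harm comes when the decision can be influenced by the results.

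The blinding in 3.1 and 3.4(3) protects each assay call. It does not extend to a decision about suitability taken once the two calls have been compared.

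Section 4.3(3) adds to the exposure. Non-conforming samples have their reasons recorded and may be re-confirmed; conforming samples get no such scrutiny. A preparation fault or degraded DNA is then more likely to be found in a discordant or failed sample, and such a fault is a ground for rejection under 7.3(1) or 7.3(2). Agreement could drift upward in this way with no bad faith by anyone. What is at stake is the headline agreement and Kappa and, if Kappa is near 0.6, the conclusion as well.

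**Working it through.** The plan gives no expected agreement, positive share, alpha or power, so there is no stated figure to reproduce. The check has two parts.

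**1. Which rule governs a tested sample?**

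| Situation | Section 4.3 | Section 7.3 | Precedence stated? |
|---|---|---|---|
| Pair disagrees; sample later judged poorly prepared or degraded | Non-conformity, 4.3(2) | Can be rejected, 7.3(1) or (2) | No |
| Kit run fails, reference confirmed; same later finding | Non-conformity, 4.3(3) | Can be rejected, 7.3(1) or (2) | No |
| Reference fails on repeat | Not covered | Rejected, 7.3(3) | No conflict |

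The third row shows that rejection under 7.3 is not confined to the time before testing. The first two rows are the gap.

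**2. How much could removal move the estimates?**

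Inputs: N = 1,000 (the minimum in 3.1). Positive share and number of discordant pairs are assumptions. Discordant pairs are split equally between the two directions, and only discordant pairs are removed.

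Formula: Kappa = (po − pe)/(1 − pe), where po is observed agreement and pe is the chance agreement from the margins.

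Base case, 50% positive, 25 + 25 discordant, so pe = 0.5 throughout:

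- None removed: po = 950/1,000 = 0.950; Kappa = (0.950 − 0.5)/0.5 = 0.900.
- 20 removed: po = 950/980 = 0.969; Kappa = 0.939.
- 30 removed: po = 950/970 = 0.979; Kappa = 0.959.

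Other positive shares, 50 discordant, 24 removed (agreement goes from 95.0% to 950/976 = 97.3% in each):

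| Positive share | Kappa before | Kappa after |
|---|---|---|
| 10% | 0.722 | 0.838 |
| 30% or 70% | 0.881 | 0.936 |
| 50% | 0.900 | 0.947 |

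Removals needed to carry Kappa from about 0.55 to just above 0.6:

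| Positive share | Discordant at start | Kappa at start | Removed | Kappa after |
|---|---|---|---|---|
| 10% | 82 | 0.544 | 16 (1.6% of N) | 0.604 |
| 30% or 70% | 190 | 0.548 | 30 (3.0%) | 0.603 |
| 50% | 226 | 0.548 | 34 (3.4%) | 0.602 |

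At the other end, 20 discordant pairs at 30% positive give Kappa 0.952; removing 10 gives 0.976. The verdict is untouched.

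Failed kit runs are shown separately, because a failed run has no cell in a two-by-two Kappa table and the plan does not say how it enters Kappa. With 20 discordant pairs among 1,000 samples, overall agreement is:

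| Failed runs | Counted as in 4.3(3) | Dropped |
|---|---|---|
| 10 | 970/1,000 = 97.0% | 970/990 = 98.0% |
| 30 | 950/1,000 = 95.0% | 950/970 = 97.9% |
| 50 | 930/1,000 = 93.0% | 930/950 = 97.9% |

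**The case against.** The best defence is that tested samples already have specific rules. Section 4.3(2) covers discordant pairs and 4.3(3) covers kit failures. The only assay failure listed in 7.3 is reference failure. The natural reading is that kit failure leads to non-conformity and reference failure to rejection, with the general clause in 7.3(1) kept for pre-analytic faults such as the one it names. Testing is blinded, an inspector is appointed (3.4(2)), and records are kept. That reading is reasonable, and it may be what the sponsor intends. It is not written down, however, and the open list leaves the other reading available.

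Three stronger readings are tempting, and the documents do not support them:

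- A reader might infer that the researcher is authorised to reject at any time, including after results exist. Section 7.3(1) is silent on timing. Its reference to continuing points to samples already entered, but an entered sample may still be unassayed. Section 3.3 (the study technology route) has no content in the text available, so a workflow figure that places the rejection step may be missing.
- A reader might infer that 7.3(1) overrides 4.3(3). No precedence is stated in either direction.
- A reader might infer that the study report would hide such removals. The records required by 4.3(3) and section 10 count against that. The supportable statement is that the protocol does not require rejected samples to be tabulated.

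The objection also succeeds on DNA quality. The numeric limits in 7.3(2) do not depend on either assay call, so the gap there is smaller and lies only in the open list and the undefined severe degradation.

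**Conclusion.** The concern holds as a gap in the rule. Researcher judgement, an open list, no timing or blinding condition, no stated precedence over 4.3 and no required accounting of rejected samples together leave result-informed removal unprevented. Its direction is known: agreement and Kappa go up.

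Its size is not known from the documents. Under the base-case assumptions, removing 20 to 30 of 50 discordant pairs adds about 2 to 3 percentage points to agreement and 0.04 to 0.06 to Kappa. That scenario removes 40% to 60% of the discordant pairs and no concordant ones, so it shows scale and is not a forecast. It does not change the Kappa > 0.6 conclusion, and no such change should be inferred from it. The conclusion is at risk only if Kappa is near 0.6, where removing 1.6% to 3.4% of samples is enough under the assumptions used. The rule should be changed because tightening it costs little and the reported agreement is otherwise exposed to bias.

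**What to change.** Reword 7.3 and add a reporting requirement:

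1. Limit rejection under 7.3(1), (2) and (4) to pre-specified sample-quality or eligibility reasons. Decide and record each rejection on the coded sample before either assay or, if the fault is found later, through someone blind to both results. The blind route means that a sample found late to be ineligible need not be kept.
2. State that 4.3(2)-(3) govern any other sample with a kit result, and that repeated reference failure under 7.3(3) is the only result-based rejection.
3. List all rejected samples by centre, with the reason and any results obtained.
4. Repeat agreement and Kappa with rejected samples included wherever both results exist.

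The cost is a wording change, a rejection log, and a few more non-conformities kept in the denominator. No assay, threshold or sample size changes.
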